Appendix F: Symptom Management During Infusion Guidelines

Adverse Reactions	Signs and Symptoms	Management
reactions are usually symptomatic and occasionally life-threatening.	
 • Disseminated-intravascular coagulation 	
 • Send recipient blood for a “transfusion reaction analysis” to the blood bank. • Consider mannitol 25 gm IV if suspicion of a transfusion ABO incompatibility reaction is high. • Consider blood cultures (and culture of the MSC product) followed by broad spectrum anti-bacterial antibiotics. • The attending BMT physician will be informed of the episode and will decide whether to restart the MSC infusion or abort the MSC infusion. • If the MSC infusion is aborted, the balance of the MSC product will be quarantined in the BMT laboratory refrigerator for possible additional analysis.
Reactions to Cryopreservatives (e.g. DMSO) DMSO is added to all MSC products being cryopreserved to protect the MSC from hypothermal damage.	
 • Metallic/garlic taste • Nausea/emesis • Flushing of face • Intestinal cramps • Acute hypertension • Bradycardia (first, second, or third degree atrioventricular block on electrocardiogram) 	
 • Pause MSC infusion. • Check vital signs and O2 saturation. • Administer additional anti-emetics if appropriate. • If bradycardia, perform an electrocardiogram. If patient is asymptomatic with first or second degree atrio-ventricular block on EKG, resume MSC infusion. If symptomatic, stop infusion and administer atropine 0.5 -1mg. • If bradycardia is present and electrocardiogram shows third degree atrio-ventricular block, consider placement of a temporary pacemaker. Consult Cardiology. • Infuse remainder of previously non-thawed MSC after reasonable resolution of the signs and symptoms of an acute DMSO reaction and acquisition of hemodynamic stability.
Infection/Endotoxemia	
 • Hypotension 	
 • Stop the MSC infusion

Appendix F: Symptom Management During Infusion Guidelines

Adverse Reactions	Signs and Symptoms	Management
The infusion of infected MSC products is usually fatal. A rapid response to the acute adverse signs/symptoms of the infusion of the infected MSC may be life-saving.	
• Fever• Oliguria/anuria• Tachycardia• Dyspnea/ hypoxemia• Disseminated intravascular coagulation• Signs/symptoms within “minutes” of MSC infusion	
• Culture the recipient’s blood and the MSC product.• Immediately start broad spectrum antibiotics. The usual default should be vancomycin, meropenem or imipenim, and tobramycin.• Use hemodynamic support as appropriate (IV fluids +/- vasopressors).• Notify the BMT laboratory clinical scientists of the suspicion of an infected MSC product.

Appendix G. Mini-Bronchoalveolar Lavage Procedure

The mini-BAL procedure involves blind specimen sampling from distal airspaces of patients with endotracheal or tracheal intubation. Specimens are obtained with the Combicath™ (Plastimed) catheter that is commonly used for the diagnosis of ventilator-associated pneumonia. The catheter is introduced from its protective sheath into the endotracheal or tracheal tube through a standard bronchoscopy adapter, and then gently advanced into the lungs until it becomes wedged in a distal airway. The catheter then is withdrawn approximately 3 cm to allow room for the inner catheter to be advanced into the distal airway. This is accomplished by removing the white protective spacer and gently advancing the inner catheter to its full length and securing it to the outside catheter by slightly twisting it into the outside catheter. Then, two 30-mL syringes containing 20 mL normal saline and a 5mL air bolus are injected rapidly into the lungs. Once the air bolus clears the second syringe, gentle aspiration is applied to the syringe for approximately 10 seconds to retrieve as much of the instilled fluid as possible (usually 5-10 ml). When completed, the catheter is removed from the endotracheal tube. The recovered aspirated samples are then emptied into a standard screw-top specimen container used for BAL samples. If the clinical condition warrants it, 1 ml can be deposited into a sterile container to be sent to the microbiology laboratory for culture.

Note: The mini- BAL procedure can be done with either one or two clinicians but it is easier to do (and typically more effective) when two clinicians are involved: one to advance, wedge, and manipulate the Combicath and the other to instill and aspirate the lavage. The patient should be pre-oxygenated on an FiO₂ of 1.0 for 10 minutes prior to the procedure and routine endotracheal suctioning should be done first to remove sputum from the airways.

After the mini- BAL, routine suction should be repeated to remove any excess BAL fluid that may be present in the airways. Assess patient's oxygenation and ventilatory status and return patient to their baseline FiO₂ when clinically indicated, usually within 5-10 minutes. The ventilator circuit should be returned to its original configuration by replacing the bronchoscopy swivel adapter with a clean adapter that was originally present in the circuit.

The mini-BAL should NOT be performed under the following circumstances:

1. FiO₂ greater than 0.70 AND PEEP greater than 14 cm H₂O
2. Hemodynamic instability (despite fluid resuscitation/pressor support)
3. Open external ventricular device or intracranial pressure greater than 15mmHg or unstable
4. Most recent INR greater than 2.0 or PTT > 40
5. Most recent Platelets less than 50x10³/mm³ (within 36 hours of BAL)

Since this is a study procedure, any associated adverse event should be reported as a study related event. Transient hypoxemia is considered an expected event for ARDS, but prolonged or severe hypoxemia following mini-BAL should be reported as an adverse event.

Appendix H. Phase 2b Investigational Product Infusion Protocol

BACKGROUND: Human mesenchymal stromal cells (hMSCs) are being tested in a placebo-controlled trial as a novel therapy for the acute respiratory distress syndrome. Several factors are essential to the safe administration of hMSCs. They include accurate identification of the donor, the recipient; the product; and the cell dose. Therapies that can damage hMSCs include hemodialysis. In addition, recognition and management of the potential side effects associated with hMSC infusion are also important.

Each study site will develop its own site-specific Standard Operating Procedure in support of this protocol. The site-specific standard operating procedure will be reviewed by the Coordinating Center prior to initiating the clinical trial at that site.

1. OBJECTIVES

- 1.1 To ensure the safe and effective infusion of either clinical grade allogeneic bone marrow-derived human mesenchymal stromal cells (hMSCs) or the placebo.
- 1.2 To ensure the administration of the full hMSC dose (10 million cells/kg predicted body weight based on cell viability at the time of initial cell preparation at UMMC).
- 1.3 To blind investigators to the product being infused (hMSCs or placebo).

2. MATERIALS/EQUIPMENT

- 2.1 250mL Normal Saline bag (delivered by BMT lab)
- 2.2 Standard blood filter tubing Y set (170-260 micron filter): At UCSF Medical Center, this is ICU Medical B9211 (delivered by BMT lab)
- 2.3 Opaque bag to blind investigational product bag (delivered by BMT lab)
- 2.4 Semi-opaque tubing sleeve to cover tubing (delivered by BMT lab)
- 2.5 Gloves (in ICU)
- 2.6 One 3-way luer stopcock (in ICU)
- 2.7 10mL luer-lock syringe (in ICU)
- 2.8 Pressure bag (in ICU) – can be used for COVID-19 patients who have their IV poles outside the room

3. POLICIES

- 3.1 A study physician from the study must initiate and be present for the entire duration of the investigational product infusion.
- 3.2 A study physician must write an order to administer the investigational product.
- 3.3 For subjects randomized to receive hMSCs, the investigational product infusion must be completed within 4 hours of the start of the cell thaw protocol. To keep study investigators blinded, the investigational product expiration time will be documented on the investigational product bag by the bone marrow transplant (BMT) laboratory staff. This time will be 4 hours to the minute after the start of the cell thaw protocol. Placebo products will be assigned a product expiration time by the BMT lab to maintain blinding. Infusion supplies

Appendix H: Phase 2b Investigational Product Infusion Protocol

will be picked up from the laboratory by a study personnel or transported to the ICU by BMT laboratory staff. Product expiration time will be documented by the BMT lab on the STAT Infusion Record and will be reviewed with study personnel. The start and end of the infusion will be documented on the STAT Infusion Record.

- 3.4 **Never discard investigational product.** In the event of an adverse reaction terminating the infusion, return any un-transfused product to the BMT laboratory immediately.
 - Note: For COVID-19 suspected or confirmed positive patients, investigational product bags and tubing do not need to be returned to the BMT Lab
- 3.5 No prophylactic pre-medications (e.g. acetaminophen or diphenhydramine) will be administered prior to the investigational product infusion. If such medications are ordered by the clinical team and given prior to or during the infusion, however, their use does not preclude proceeding with the infusion.
- 3.6 The following medications should be immediately available at the patient's bedside during the infusion and the post-infusion monitoring period: epinephrine 1 mg for intravenous administration, hydrocortisone 100 mg for intravenous administration, and diphenhydramine 50 mg for intravenous administration.
- 3.7 The investigational product can be infused via peripheral or central venous access. If peripheral, the IV should preferably be 18 gauge, but no smaller than 20 gauge.
- 3.8 Ideally a separate port or line should be used for the investigational product infusion. The infusion should not be "piggy backed" into a medication line. If absolutely necessary, a stopcock can be used at the lumen connection to create a separate, dedicated line for the investigational product infusion. Avoid administration with dextrose containing solutions; Normal saline, Plasmalyte, and Lactated Ringers are acceptable.
- 3.9 Dialysis Patients: Patients receiving intermittent dialysis may be dialyzed prior to the investigational product infusion, but should not be dialyzed until 24 hours or more after receiving the infusion if possible. Continuous renal replacement therapy will be allowed to continue during the hMSC or placebo infusion.
- 3.10 Positioning: Patients must remain in the supine or prone position for the duration of the infusion and the post-infusion observation period.
- 3.11 Apply standard precautions and aseptic technique at all times.
- 3.12 Verify patient's identity per National Patient Safety Goals (two identifiers). (At UCSF Medical Center, the Department of Nursing Blood and Blood Components Administration Procedure should be followed).
- 3.13 Monitor the patient for reaction to the investigational product infusion during administration (see **Appendix F** for potential side effects and symptom management guidelines).

4. PROCEDURE

- 4.1 Study Physician to write order for investigational product infusion. This order also confirms the date, and time of the investigational product infusion. No investigational product will be thawed, processed, or released from the BMT laboratory without this order. (At UCSF Medical Center: Fax infusion order to BMT Lab, [contact]. Confirm infusion time with BMT laboratory at [name]).
- 4.2 Personnel from the BMT lab will set up IV tubing as follows: 250mL normal saline bag spiked on to one limb of "Y-set" standard blood filter tubing (170 - 260 micron filter tubing,

Appendix H: Phase 2b Investigational Product Infusion Protocol

for example ICU Medical B9211). The BMT lab will saline prime the blood filter tubing setup. The IV tubing will be covered with the blinding sleeve.

4.3 The investigational product will be administered as 300 mL in a 300 mL transfer bag; this bag will be covered with an opaque bag to blind investigators to the content. The BMT laboratory will label both the transfer bag and the blinding bag with the patient identifiers, then spike the investigational product bag onto the saline-primed IV tubing.

4.4 The Study Physician will:

- Confirm that the patient has met criteria to receive the investigational product infusion: in addition to meeting inclusion criteria and having no exclusion criteria, the 2 hour stable baseline period must have been achieved, and the PaO₂/FiO₂ ratio on a blood gas obtained within 90 minutes of starting the baseline stability period cannot equal or exceed 250. If the PaO₂/FiO₂ ratio is equal or greater than 250, the patient is no longer eligible to receive the investigational product.
- Follow National Patient Safety Goals to identify the patient (two identifiers). (At UCSF Medical Center: Verify patient identification per Department of Nursing Blood and Blood Components Administration Procedure).
- Verify that the signed consent is in the patient's medical record.
- Review the infusion order.
- BMT lab personnel or a study physician will review the information on the investigational product bag with the bedside RN or study physician for the following:
 - Recipient name/medical record number (MRN)
 - Recipient date of birth
 - Product expiration date/time
 - Product identification number
 - Product volume

One person should read the information on the product and a second person should compare it with the information on the paperwork and patient identification band. One of these two individuals should be a study investigator.

- Prior to infusion, the study physician should ensure that the following medications are available at the patient's bedside:
 - Epinephrine: 1 mg
 - Hydrocortisone: 100 mg
 - Benadryl: 50 mg

4.5 The study physician will be present for the entire infusion procedure:

- The investigational product bag will arrive from the BMT lab already spiked and attached to the saline-primed tubing, and covered with the semi-opaque sleeve.
 - The investigational product can be infused immediately after the product arrives at the bedside from the BMT laboratory and all patient checks have been completed. There is no need to wait for the bag to come to room temperature.
- For COVID-19 patients with the IV pole outside of the patient's room, the study personnel can wrap the investigational product with a pressure bag.
- The study physician will attach the primed filter tubing to a three-way stopcock and the intravenous line through which the investigational product is to be infused.

Appendix H: Phase 2b Investigational Product Infusion Protocol

- Do NOT use bifuse tubing. DO NOT INFUSE THROUGH A NEEDLELESS CAP.
- The study physician will confirm that all IV connections are secure and that the infusion lines from the investigational product bag to the patient are visible but covered with the semi-opaque sleeve.
- Document the start date and time of the investigational product infusion on the STAT Infusion Record.
- If there is accidental unblinding, contact CCC and the investigator on-call to discuss how to proceed.

4.6 Start the infusion:

- At each center, the priming volume of the filter set must be measured and infusion drip rates should be calculated prior to enrollment of the first study patient:
 - For example, for ICU Medical B9211, the priming volume is 16.9 mL. The # drops/mL for this filter set per the manufacturer is approximately 10.
 - The drip chamber should not be primed to “full” since the infusion rate will be set based on the number of drops/minute that are used
 - The clamps CAN be opened and closed through the blinding tubing. If you are having difficulty opening and closing the clamps, however, you can cut a small vertical hole in the sleeve to allow direct access to the clamp.
- Run the entire volume of investigational product (300 mL) at the same rate over 60 minutes, checking the drop rate at the start of the infusion, approximately 5 minutes later, and periodically throughout the infusion. These can be visualized through the semi-opaque tubing sleeve. The drop rate should be checked by counting the number of drops over 30 seconds and calculating the number of drops/minute.
 - If using a pressure bag, pump the bag until the target drop rate is reached.
- For the ICU Medical B9211 filter set:
 - The target infusion drop rate is 40 drops/30 seconds for the entire infusion
 - Continue checking the drop rate periodically throughout the infusion. If the infusion drop rate falls to 20-25 drops/30 seconds, increase the drop rate back to 40 drops/30 seconds.

4.7 **Do not run normal saline concurrently with the investigational product.**

4.8 **When the investigational product bag is empty, proceed to the RINSE AND FLUSH PROCEDURES (4.12) to rinse the bag and flush the line.**

4.9 If the investigational product does not infuse easily by gravity or using a pressure bag, you may attempt to attach the luer-lock syringe to the three-way stopcock and push the investigational product through line slowly (2-5 mL/min) via a syringe.

4.10 We do not anticipate that clumping should be an issue. However, save original filter set for the bone marrow transplant laboratory; they should visually examine the filter set for clumping prior to disposal. If clumping is significant and leads to unblinding of the bedside investigator or is noted by the BMT laboratory, contact the CCC and the investigator on call immediately.

Note: For COVID-19 suspected or confirmed positive patients, investigational product bags and tubing do not need to be returned to the BMT Lab

4.11 Monitoring:

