Appendix H: Phase 2b Investigational Product Infusion Protocol

- Blood pressure, heart rate and oxygen saturation will be continuously monitored for the duration of the infusion and documented every 15 minutes during the infusion.
- An arterial blood gas will be obtained within 90 minutes prior to beginning the baseline stability period and within 15 minutes of the end of the infusion. If the PaO₂/FiO₂ ratio on the blood gas obtained during the baseline stability period is greater than 250, the patient should NOT receive the investigational product.
- See **Appendix F** for potential side effects of the infusion. Monitor periodically during the infusion for these side effects. If the patient experiences significant side effects, consider pausing or stopping infusion.

4.12 RINSE AND FLUSH PROCEDURE: Approximately **100 mL of saline total should be used to rinse the investigational product bag and flush the line**, ensuring that the investigational product has been rinsed from the bag and infused through the priming setup.

- At the end of the infusion, rinse the investigational product bag with normal saline using this protocol. To do this: (1) Clamp the investigational product line to the patient (2) Unclamp the saline line and lower the investigational product bag to allow for saline to enter the investigational product bag; (3) After a small amount of saline (approximately 20 mL) has entered the investigational product bag, reclamp the saline line; (4) Swirl the saline in the investigational product bag; (5) Re-hang the investigational product bag, then open the line and infuse the saline rinse from the investigational product bag into the patient until the bag is empty; (6) Finally, allow 80 mL of saline to run through the filter to flush the remaining rinse volume into the patient. **The rinse will include 100 mL used to flush the bag and will be infused over 12-15 minutes:**
 - $100 \text{ mL} * 10 \text{ drops/mL} = 1000 \text{ drops}/(80 \text{ drops}/\text{minute}) = 12.5 \text{ minutes}$
 - **The target infusion rate for the rinse and flush is 40 drops/30 seconds (same as the start of the infusion) and the infusion should be complete in 12-15 minutes**
 - Note: If using a pressure bag, after the initial 20 mL of saline has been infused, the next 80 mL of saline needs to be manually pushed with a syringe.

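### Protocol Appendix H, step 4.6: the drop rate set for the B9211 filter set empties the 300 mL bag in 37.5 minutes, not the 60 minutes the same step requires

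*Protocol*

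**What the plan says.** Appendix H, step 4.6 gives four instructions that bear on infusion speed.

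- Volume and time: "Run the entire volume of investigational product (300 mL) at the same rate over 60 minutes".
- Drop factor for the ICU Medical B9211 set: "The # drops/mL for this filter set per the manufacturer is approximately 10".
- Target for that set: "The target infusion drop rate is 40 drops/30 seconds for the entire infusion".
- Correction rule for that set: "If the infusion drop rate falls to 20-25 drops/30 seconds, increase the drop rate back to 40 drops/30 seconds".

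Step 4.12 sets the rinse and flush at 100 mL over 12 to 15 minutes. It uses the same 40 drops/30 s, describes that as the rate at the start of the infusion, and shows the drop-count sum behind the time.

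Protocol Sections 8.9 and 9.4, Appendix E (Background) and SAP Section 5 all give 60 to 80 minutes for the infusion, with "approximately" attached in Section 9.4 and SAP Section 5.

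On scope, Appendix H item 2.2 names the B9211 as the set used at UCSF Medical Center. Step 4.6 says of each center that "infusion drip rates should be calculated prior to enrollment of the first study patient", and the Background of Appendix H says "Each study site will develop its own site-specific Standard Operating Procedure in support of this protocol".

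**The concern.** Step 4.6 gives the bedside team a time and a drop count for the same bag, and the two look incompatible. The drop count is what is checked during the infusion, so it is likely to win. A site following it would infuse faster than the protocol states, and the correction rule would push a rate that meets the 60 minutes back up. Any site that copied the B9211 figures into its own procedure would carry the error over.

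Infusion speed bears on risks the protocol itself lists: transient occlusion of the pulmonary microcirculation (Section 3.7.2.2), and volume overload and DMSO reactions (Appendix F). The phase 1 experience described in Section 3.6 was with infusion over one hour.

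**Working it through.** **Inputs.** Product volume 300 mL and stated time 60 min (step 4.6). Drop factor about 10 drops/mL and target 40 drops/30 s, or 80 drops/min (step 4.6, B9211). Rinse 100 mL over 12 to 15 min (step 4.12). Overall window 60 to 80 min (Sections 8.9 and 9.4, Appendix E, SAP Section 5).

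**Formula.** Time = volume × drops per mL ÷ drops per minute. This is the sum shown in step 4.12.

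**Reproducing the plan's own figure.** Rinse: 100 × 10 ÷ 80 = 12.5 min. This matches step 4.12, so the formula and drop factor are being read as intended.

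**Product at the target rate.** 300 × 10 ÷ 80 = 37.5 min. The flow is 80 ÷ 10 = 8 mL/min, against 300 ÷ 60 = 5 mL/min. The ratio is 8 ÷ 5 = 1.60. For comparison, the slow syringe push in step 4.9 is limited to 2 to 5 mL/min.

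**Product plus rinse.** 37.5 + 12.5 = 50 min, or 37.5 + 15 = 52.5 min. Both are below 60.

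**Rate that gives 60 minutes.** 300 × 10 ÷ 60 = 50 drops/min = 25 drops/30 s.

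**Correction rule.**

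| Drops/30 s | Product time (min) | Under the rule |
|---|---|---|
| 20 | 3000 ÷ 40 = 75 | raise to 40 |
| 25 | 3000 ÷ 50 = 60 | raise to 40 |
| 26 | 3000 ÷ 52 = 57.7 | leave |
| 40 | 3000 ÷ 80 = 37.5 | target |

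Every whole-number rate from 26 to 40 that the rule leaves alone gives less than 60 minutes for the product.

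**Can anything in the stated inputs recover 60 minutes?**

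- Drop factor: 60 min at 80 drops/min needs 80 × 60 ÷ 300 = 16 drops/mL. An assumed range of 9 to 12 drops/mL gives 300 × 9 ÷ 80 = 33.8 min to 300 × 12 ÷ 80 = 45 min.
- Priming volume: 16.9 × 10 ÷ 80 = 2.1 min. The set arrives primed with saline, so this is only the lag before the last product clears the line, and it falls within the rinse.
- Drift: if the rate falls evenly from 40 to 20-25 drops/30 s between checks (an assumption), the mean is 30 to 32.5. Product time is then 3000 ÷ 60 = 50 min to 3000 ÷ 65 = 46.2 min.

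None of these reaches 60 minutes for the product.

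**The case against.** The strongest counter-argument concerns reach. A gravity drip may not hold 40 drops/30 s, and the correction rule itself expects the rate to fall. Under even drift to 20-25 the product takes 46.2 to 50 min. Adding a rinse of 12.5 to 15 min gives 58.7 to 65 min, at or near the lower end of an approximate 60 to 80 minutes. More generally, with a 12.5-minute rinse the total is below 60 only when the mean rate exceeds 3000 ÷ 47.5 ÷ 2 = 31.6 drops/30 s. Handling the bag for the rinse also takes time that the sum leaves out. The documents do not say whether the 60 to 80 minutes includes the rinse.

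This stands in part: the conflict with the 60 to 80 minutes depends on the rate actually delivered. It does not rescue step 4.6, which asks for one constant rate, assigns 60 minutes to the 300 mL alone, and has the rinse begin only once the bag is empty (step 4.8). With the target held, the total is short whether the window includes the rinse (50 to 52.5 min) or not (37.5 min).

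It is also fair that the B9211 is one set. A center that calculates its rate from 300 mL over 60 minutes gets the right answer, and the Coordinating Center reviews each site's procedure before the site starts. The documents do not say which sites other than UCSF use this set.

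Finally, the practical consequence shown is limited. No maximum rate is set, nothing in the documents shows 8 mL/min to be harmful, and a study physician is present throughout. Endpoint times run from the start of the infusion, so a shorter infusion does not move them.

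**Conclusion.** The concern holds. For the B9211 set, step 4.6 contradicts itself: its drop target gives 37.5 minutes (8 mL/min) where its stated time needs 60 (5 mL/min), a rate 60% too fast. Its correction rule treats the right rate as a fault. This rests on the stated drop factor of about 10 and on the target being held. Drift narrows the gap but does not close it for the product, and no plausible error in the drop factor explains it.

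The shortfall against the 60 to 80 minutes elsewhere is 7.5 to 10 minutes when the target is held, and may vanish if the rate sags enough between checks.

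This is a matter of dosing procedure. Both arms receive 300 mL under the same instruction, and the sample size and primary analysis are untouched. It should be corrected because staff using this set cannot follow both instructions.

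**What to change.** In step 4.6, change the B9211 target to about 25 drops/30 s (50 drops/min, 5 mL/min) and lower the correction trigger to clearly below 25. A trigger near 20 is workable: even drift from 25 to 20 averages 22.5, so the product takes 3000 ÷ 45 = 66.7 min and the total is 79.2 min with a 12.5-minute rinse (81.7 with 15). For reference, the total passes 80 minutes when the mean rate falls below 3000 ÷ 67.5 ÷ 2 = 22.2 drops/30 s with a 12.5-minute rinse, or 3000 ÷ 65 ÷ 2 = 23.1 with a 15-minute rinse. The protocol should say whether its window includes the rinse.

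In step 4.12, state the rinse rate on its own and remove the cross-reference to the starting rate. At 40 drops/30 s the rinse still takes 12.5 min; at 25 it would take 1000 ÷ 50 = 20 min and miss its 12 to 15. The corrected total with the target held is 60 + 12 to 15 = 72 to 75 min, so the durations in Sections 8.9 and 9.4, Appendix E and SAP Section 5 can stay.

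If 8 mL/min is clinically intended, keep the drop count and correct the durations instead. That choice is the investigators'.

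Either way, notify sites that use or copied the B9211 figures, and compare the start and end times already kept on the STAT Infusion Record (Appendix H, 3.3) with the stated duration. The cost of the rate correction is two short edits in Appendix H, revision of the affected site procedures, a notice and a brief review of recorded times. There is no statistical cost.
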